13.4 Analysis of Secondary and Tertiary Endpoints

General linear models and nonparametric approaches will be used to analyze the continuous outcomes. For binary outcomes, logistic regression analysis will be used to compare each treatment vs. placebo and estimate the odds ratio and 95% confidence interval for low-dose dopamine vs. placebo and low-dose nesiritide vs. placebo comparisons. Time-to-event comparisons will be conducted using Kaplan-Meier curves and log-rank tests. For analyses of patient global well being VAS and dyspnea VAS, the value of zero will be imputed for all measurements missing due to death. Sensitivity analyses, including the worst-rank score analysis ⁽²¹⁾ will be employed to assess the influence of informatively missing values on the results. In particular the worst-rank score analysis will account for missing data due to deaths.

13.5 Exploratory Analyses

Analyses comparing the low-dose dopamine and low-dose nesiritide groups will be considered exploratory as they do not directly address the two primary hypotheses of ROSE. However, if both the low-dose dopamine and low-dose nesiritide treatment are statistically superior to placebo, a secondary analysis will be conducted to compare the two active treatment arms.

Further analyses will be conducted to determine whether the effect of low dose dopamine or low dose nesiritide is modified by each of the following covariates:

- Admission blood pressure
- Age (≤ 70 v. > 70)
- Pre-randomization GFR

Estimation of subgroup effects will be conducted within the linear models framework.

For each of the three treatment groups, the relationship between baseline GFR and 72 hour cumulative UV will be estimated using linear regression models. Additional analyses will compare the placebo subjects randomized to the dopamine strategy vs. the placebo patients randomized to the nesiritide strategy to determine whether the presence of the PICC line alters patient outcomes.

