5. BASIC STUDY DESIGN

This study is a randomized, double blind, placebo controlled, multi-center clinical trial of patients with signs and symptoms consistent with AHF within 24 hours of hospital admission. A total of approximately 360 patients will be enrolled in the trial.

Patients will be randomized to one of 3 treatment regimens (120 patients / treatment regime):

- 1. Optimal diuretic dosing + placebo
- 2. Optimal diuretic dosing + low dose dopamine
- 3. Optimal diuretic dosing + low dose nesiritide

Central venous line or PICC line or standard peripheral IV catheter placed in the antecubital fossa, depending on local hospital requirements, will be placed in the patients randomized to the Dopamine strategy group. Standard peripheral IV catheter will be placed in the patients randomized to the Nesiritide strategy group

ROSE protocol Amendment 1: March 24, 2011

TThere will be an initial open 1:1 randomization to a Nesiritide Strategy group or a Dopamine Strategy group. Patients in the Dopamine Strategy group will subsequently be randomized to low dose dopamine or placebo in a 2 to 1 blinded fashion. Likewise patients in the Nesiritide Strategy group will be randomized to low dose nesiritide or placebo in a 2 to 1 blinded fashion. All patients will receive open-label diuretic treatment.

Figure 4

For testing the primary hypotheses outlined in Section 2.1, the placebo patients will be pooled, so that patients randomized to receive dopamine will be compared with the pooled placebo group, and similarly, patients randomized to receive nesiritide will be compared to the pooled placebo group.

The study treatment regimen will be administered for *a total duration of* 72 hours, unless clinical reasons require discontinuation earlier.

The investigator may modify the diuretic dose at 24 and / or 48 hours. The primary assessment for both efficacy and safety will occur at 72 hours after randomization. **After** the primary assessment at 72 hours, all treatment will be open label at the treating physician's discretion.

The primary safety endpoint will be change in serum cystatin C from randomization to 72 hours, based on a standardized, blinded core lab assessment. The primary endpoint for efficacy will be cumulative urinary volume (UV; indwelling urinary catheter) at 72 hours.

Patients will be followed daily during hospitalization for assessment of serious adverse events.

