6. STUDY POPULATION AND ELIGIBILITY CRITERIA

6.1 Inclusion Criteria

- A diagnosis of heart failure as defined by the presence of at least 1 symptom (dyspnea, orthopnea, or edema) AND 1 sign (rales on auscultation, peripheral edema, ascites, pulmonary vascular congestion on chest radiography)
- Prior clinical diagnosis of heart failure Must be identified within 24 hours of hospital admission (24 hour clock begins when the admission orders are placed)
- Estimated GFR of \geq 15 but \leq 60 mL/min/1.73m² determined by the MDRD equation
- Male or female patient ≥18 years old
- Willingness to provide informed consent
- Ability to have a PICC or central line placed (if needed) within 12 hours of randomization and study drug infusion started
- Anticipated hospitalization of at least 72 hours

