7.1 Randomization to 24 hours

Patients will be randomized as described above to one of 3 treatment combinations:

- Optimal diuretic dosing + placebo
- Optimal diuretic dosing + low dose dopamine
- Optimal diuretic dosing + low dose nesiritide

All patients will be started on a 2 liter per day fluid restriction and a 2 gm per day sodium diet. Decisions regarding the use of standard heart failure medications such as ACE inhibitors, beta blockers and digoxin will be left to the discretion of the treating physicians.

Vascular access

Central venous line or PICC line or standard peripheral IV catheter placed in the antecubital fossa, depending on local hospital requirements, will be placed in the patients randomized to the Dopamine strategy group. Standard peripheral IV catheter will be placed in the patients randomized to the Nesiritide strategy group

Urinary Catheter

Use of an indwelling urinary catheter will be encouraged in all patients but a patient may decline and remain in study.

Study Drug Dose and Supplies

The study site investigational pharmacy will prepare low dose dopamine $(2\mu g/kg/min)$, low dose nesiritide $(0.005 \mu g/kg/min without bolus)$ or placebo (Dextose 5% water). Hospital stock should be used. Clinical personnel, investigators, and the patients will be blinded.

Based on the results from the recently completed DOSE study, the optimal dose of diuretic will be as follows:

IV furosemide (or equivalent) at a dose equivalent to 2.5 x the total daily *outpatient* oral furosemide (or furosemide equivalent) dose twice daily or equivalent dosing over a 24 hour period. The maximum total daily dose to be administered is 600 mg. and the

minimum total daily dose to be administered is 80 mg. (at frequency determined by the local physician). For patients who have not been taking outpatient loop diuretics, they will receive 80 mg/day of IV furosemide (or equivalent) dose. If the outpatient dose has changed over the week prior to admission, the outpatient dose will be defined as that being utilized 7 days prior to randomization. For patients receiving outpatient loop diuretics other than furosemide, conversion to furosemide equivalents will be as follows:

1 mg torsemide = 2 mg furosemide

1 mg bumetanide = 40 mg furosemide

At 24 hrs, the treating physician can chose to change the diuretic dose

- a. Continue current dose without change
- b. Decrease diuretic dose
- c. Increase diuretic dose
- d. Change to oral diuretic

7.2 48 hours

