9.1 Randomization

After providing informed consent and signing the ICF, all study subjects will be randomized using procedures determined by the DCC to one of 3 treatment groups. **Patients will be randomized to the nesiritide or dopamine strategy in a 1:1 allocation ratio.** Within each strategy, subjects will be randomized to active drug vs. placebo in a 2:1 allocation ratio. A permuted block randomization method stratified by site will be used to ensure relatively equal distribution of subjects to each arm within each clinical site.

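### The exploratory placebo-versus-placebo comparison in section 13.5 is labelled a test of the PICC line, but the access rules make it a comparison of strategies

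*Protocol*

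**What the plan says.** Among the exploratory analyses, section 13.5 plans to "compare the placebo subjects randomized to the dopamine strategy vs. the placebo patients randomized to the nesiritide strategy", and gives the purpose as "to determine whether the presence of the PICC line alters patient outcomes".

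The access rules are in sections 5 and 7.1, in the same words. For the dopamine strategy: "Central venous line or PICC line or standard peripheral IV catheter placed in the antecubital fossa, depending on local hospital requirements". For the nesiritide strategy: "Standard peripheral IV catheter will be placed in the patients randomized to the Nesiritide strategy group". The eligibility criterion in section 6.1 is also conditional: "Ability to have a PICC or central line placed (if needed) within 12 hours of randomization".

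Section 5 makes the first randomisation, to strategy, open. Only the second step, active drug or placebo, is blinded. Section 7.4 ties stopping and restarting the infusion to blood pressure and symptoms in the nesiritide strategy and to heart rate in the dopamine strategy.

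**The concern.** The stated purpose treats assignment to the dopamine strategy as if it meant having a PICC. Under sections 5 and 7.1 it does not. Some dopamine-strategy placebo patients may have a PICC, some another central line, and some the same kind of peripheral access as the group they are compared with. Section 13.5 neither restricts nor classifies patients by access.

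What is at stake is how this one exploratory result is read. A null result could be reported as showing no PICC effect when it may only reflect how few patients had one. A positive result could be blamed on the line when it came from something else that differs between the strategies.

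**Working it through.** **1. The plan's own figures.** A two-sample t-test (noncentral t, two-sided alpha 0.025) reproduces section 13.3. Urine volume with 108 per arm and SD 2900 mL gives 90.1% power for 1400 mL and 80.0% for 1224 mL (stated: 90% and 80%). Cystatin C with 102 per arm, SD 0.62 mg/L and a difference of 0.3 mg/L gives 88.3% (stated: 88%). The protocol gives no figure for the placebo-versus-placebo contrast.

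**2. Size of the contrast.** Section 5: "A total of approximately 360 patients will be enrolled in the trial", split 1:1 between strategies. Section 9.1: "Within each strategy, subjects will be randomized to active drug vs. placebo in a 2:1 allocation ratio". Placebo patients per strategy: 360 / 2 / 3 = 60. The missing-data limits in section 13.3 (10% for urine volume, 15% for cystatin C) leave 60 × 0.90 = 54 and 60 × 0.85 = 51 evaluable.

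**3. What the contrast estimates.** Let q be the share of dopamine-strategy placebo patients with central or PICC access, and L the effect of such a line. Then

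expected difference = q × L + (effect of all other strategy differences).

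The protocol does not give q, so it is varied from 0 to 1. It suggests no value for L either. For illustration L is set to 1400 mL or 0.3 mg/L, borrowed from the drug-effect power calculation. The other strategy differences are set to zero.

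**4. Power.** Alpha is 0.05 two-sided (the default in section 13.1). For urine volume the standard error is 2900 × √(2/54) = 558 mL. At q = 1 the noncentrality is 1400/558 = 2.51; at q = 0.5 it is 700/558 = 1.25.

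| q | Expected difference in urine volume (mL) | Power, urine volume (54 vs 54) | Expected difference in cystatin C (mg/L) | Power, cystatin C (51 vs 51) |
|---|---|---|---|---|
| 1 | 1400 | 70% | 0.30 | 68% |
| 0.75 | 1050 | 46% | 0.225 | 44% |
| 0.5 | 700 | 24% | 0.15 | 23% |
| 0.25 | 350 | 10% | 0.075 | 9% |
| 0 | 0 | 5% | 0 | 5% |

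Even at q = 1 the 95% confidence interval for urine volume has a half-width of 1.98 × 558 ≈ 1,106 mL.

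**5. What a line-specific analysis could deliver.** Take q = 0.5 and suppose it arises because hospitals with half the patients require central or PICC access and the others use none.
- Only hospitals that require it, 27 vs 27: standard error 2900 × √(2/27) = 789 mL, noncentrality 1400/789 = 1.77, power 41%. The 95% interval half-width is 2.01 × 789 ≈ 1,584 mL.
- Strategy-by-hospital-requirement interaction: standard error 2900 × √(4/27) = 1,116 mL, noncentrality 1400/1,116 = 1.25, power 24%. This equals the power of the diluted overall contrast at q = 0.5.

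**6. Link to the primary model.** The model in section 13.2 carries an indicator for strategy as well as for treatment. Dopamine is given only in the dopamine strategy and nesiritide only in the nesiritide strategy. With those indicators and no other covariates, the fitted mean for placebo is a in the nesiritide strategy and a + s in the dopamine strategy. The strategy coefficient s is therefore the difference between the two placebo means. A check on simulated data with 60 placebo and 120 active patients per strategy gave exact agreement.

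**The case against.** The best defence is that the comparison itself is sound. It sets two randomised placebo groups side by side, it is labelled exploratory, and no primary or secondary conclusion depends on it. Only the clause naming its purpose is inexact, and nothing in section 13.5 commits the sponsor to reporting a null result as proof that the PICC is harmless. How access is classified might also be left to the analysis plan. All this limits the point to one of interpretation. It does not remove it, because the purpose is stated in the protocol and conflicts with the protocol's own access rules.

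The figures are also open to challenge, fairly. Both q and the 1400 mL line effect are assumptions, and nothing in the protocol suggests that a catheter changes urine volume by that much. With perfect labelling (q = 1) power would still be only 70%, so a null result would be inconclusive anyway.

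Two stronger readings are tempting and not supported. A reader might infer that this is the plan's only check on pooling the placebo groups. It is not: the strategy coefficient in the section 13.2 model estimates the same difference. A reader might also infer that an amendment loosened the access rule and left section 13.5 behind. The superseded text is not shown, and the conflict within the current text does not depend on that history.

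**Conclusion.** The point holds as a mismatch between a stated purpose and the contrast meant to serve it. The comparison is valid as a randomised comparison of strategies among placebo patients. It is not a test of the PICC line, because access in the dopamine strategy varies by hospital and the strategies differ in open assignment and in stopping rules as well.

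The loss can be illustrated but not fixed as a number. For an assumed 1400 mL line effect, power runs from 70% when all have central or PICC access to 24% at half and 5% at none, given SD 2900 mL, 54 evaluable patients per group and no other strategy effect. The importance is minor: the primary conclusions are untouched, but the correction costs very little.

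**What to change.** Reword section 13.5 in two parts.

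1. Describe the overall contrast as a strategy-level comparison of the two placebo groups, reported with a confidence interval, and say that it is the same quantity as the strategy coefficient in the section 13.2 model.
2. Examine a central or PICC line effect only descriptively, by comparing the two placebo groups within hospitals whose requirements, in place before randomisation, mandate central or PICC access for dopamine. Section 9.1 states that "A permuted block randomization method stratified by site will be used", so this comparison remains randomised. Grouping patients by the access they received would not. Give a confidence interval, and state that precision is low (about 41% power for 1400 mL in the illustrative 27 vs 27 case) and that the other strategy differences remain.

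An interaction test between strategy and hospital requirement is best left out. If it is kept, label it as having about 24% power in the same scenario.

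The cost is a few sentences and one site-level variable, the hospital's access requirement. Nothing changes in treatment, access rules or sample size.

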13.6 Statistical Monitoring Plan

Interim data analysis for efficacy will not be conducted due to relatively small size and short duration of this phase II clinical trial. Safety data will be periodically assessed by the Data and Safety Monitoring Board based on reporting of adverse events and treatment-level summary data.

14. DATA MANAGEMENT PROCEDURES

ROSE-AHF is a prospective, randomized, controlled study where data will be collected, analyzed, and interpreted by the Duke Clinical Research Institute which functions as the DCC for the Heart Failure Network. Data other than safety data cannot be used for publication or reporting outside of this study until the study is completed or discontinued by the DSMB or Heart Failure Network. This is necessary since dissemination of preliminary information may inappropriately affect the objectivity of the study. For this reason Study Investigators or other parties will not be allowed to perform subset analyses at any point before the conclusion of this study.

All prospective publications or presentations must be reviewed and approved by the Heart Failure Network Publications and Steering Committees.

15. STUDY ADMINISTRATION

15.1 Data and Safety Monitoring Board (DSMB)

A DSMB will be appointed by the NHLBI. This will be a group of individuals with pertinent expertise in heart failure and clinical trials. The DSMB will advise the sponsor regarding the continuing safety of current participants and those yet to be recruited, as well as the continuing validity and scientific merit of the trial.

15.2 Data Coordinating Center

The Duke Clinical Research Institute will function as the Data Coordinating Center (DCC) for this trial as specified by the NHLBI.

15.3 Core Laboratories

This study will utilize a biomarker core laboratory designated by the NHLBI and the DCC. Plasma specimens at baseline, 24 hours, 48hours, 72 hours, day 7 (or discharge if earlier) will be processed according to the procedures provided by the core laboratory and sent to the core laboratory on dry ice for analysis. These tests will include those agreed upon by the Heart Failure Network Biomarker Working Group

Urine collection: We will collect five (5) urine samples: Baseline, 24, 48, 72, day 7 or discharge if earlier for assay of selected urinary biomarkers determined by the Heart Failure Network Biomarker Working Group. These urine samples will be obtained as close as possible to (if not simultaneous with) collection of serum biomarkers. Collection should come from clean voided urine or Foley catheter. Samples will be sent to the Biomarker Core Facility for processing.

17. APPENDICES

	Baseline	24 hours (+ / -) 2 hrs	48 hours (+ / -) 2 hrs	72 hours	Day 7 or discharge	60 days (+ / -) 7 days	6 months (+/-) 7 days
Informed Consent	Х						
History and physical	Х	X	Х	Х	X		
CV Medication History	Х	X	Х	Х	X		
Vital Signs	Х	X	Х	Х	Х		
Oxygen saturation	Х	X	Х	Х	X		
Body weight	Х	X	Х	Х	X		
VAS for PGA	Х	X	Х	Х			
VAS for Dyspnea	Х	X	Х	Х			
Urine output and Fluid		X	Х	Х			
balance/24 hours							
Cr, BUN, electrolytes	Х	X	X	Х	X		
Plasma collection for HFN Biomarkers	Х	X	X	Х	X		
Urine Biomarkers	Х	X	Х	Х	X		
Urine collection for UNaV		X	х	Х			
Serious Adverse events		X	X	Х	X		
Rehospitalization Check						X	
Phone visit to assess vital status						X	Х

17.1 Appendix A. Schedule of Assessments

17.2 Appendix B. List of Abbreviations

ACEangiotensin-converting enzymeADHFacute decompensated heart failureAHFacute heart failureAICDsautomatic implantable cardioverter-defibrillatorsAUCarea under the curveBNPB-type natriuretic peptideCOcardiovascular flowCRPC-reactive proteinCRSCardio-renal syndromeDOSEDiuretic Optimization Strategies EvaluationEDEmergency DepartmentEFejection fractionJVPJugular venous pressureLVEDPleft ventricular end diastolic pressureLVEFleft ventricular eigection fractionIVIntravenousNIVnoninvasive positive pressure ventilationNYHANew York Heart AssociationPGAPatient global assessmentPACpulmonary artery catheterPCWPPulmonary capillary wedge pressureRBFrenal blood flowSVRsystemic vascular resistanceUSUnited StatesVASvisual analogue scaleUVurinary volume
--

Site Number:	Patient Number:

Assessment Date: __(day)/__(month) ____(year) Time: __: __

17.3 Appendix C. VAS Instruments

VAS – Global Well Being (PGA)

Please draw a line on the scale to show how you feel right now. The number "0" equals the worst your have ever felt and the number "100" equals the best you have ever felt.

100 = Best you have ever felt

0 = Worst you have ever felt

Site Number: _ _ _ Patient Number: _ _ _ - _ _ _

Assessment Date: __(day)/__(month) ____(year) Time: __: __

VAS - Dyspnea

Please draw a line on the scale to show how your breathing feels right now. The number "0" equals the worst your breathing has ever felt and the number "100" equals the best your breathing has ever felt.

100 = I am not breathless at all

0 = I am as breathless as I have ever been

17.4 Appendix D. Informed Consent Form

Separate attachment.
